At each clinic visit the patient will be reminded of the importance of taking the study medication exactly as prescribed. The study drug will be supplied in prescription vials or bottles containing adequate study medication to last until the next scheduled clinic visit. Patients will be instructed to return each vial or bottle at the next clinic visit. Capsule counts will be made, with or without the patient's knowledge (at discretion of study personnel), as a means of assessing patient compliance. Patients taking 90-110% of the capsules prescribed will be considered compliant. Patients will also be questioned about any non-study medications that have been taken since the previous visit and will be reminded of any drugs that should be avoided.

Tolerance to the study medication during the titration period will be monitored by the cochairman. Periodic calls will be made to each center to evaluate their titration efforts and to counsel centers with problems.

B. Monitoring Adverse Treatment Effects

1. Adverse Experiences

This study will be conducted under an IND (Investigational New Drug Application) sponsored by the VA Cooperative Studies Program. Monitoring and reporting adverse experiences will comply with FDA requirements. Patients will be closely monitored at each visit for adverse experiences possibly due to study participation. An adverse experience is defined as any adverse change from the patient's baseline condition, including any clinical or laboratory test value abnormality that occurs during the course of the study, regardless of its association with the study medication. All unexpected events or adverse experiences that occur during the study period, regardless of their association with the study medication, will be reported on the "Adverse Events" form. An assessment of medication relatedness will be required for each event reported.

2. Immediately Reportable Adverse Experiences

ANY ADVERSE EXPERIENCE CONSIDERED TO BE SERIOUS OR UNEXPECTED (PREVIOUSLY UNREPORTED) AND POSSIBLY OR PROBABLY RELATED TO THE STUDY MEDICATION REQUIRES PROMPT NOTIFICATION OF THE STUDY CO-CHAIRMEN AND CLINICAL RESEARCH PHARMACIST. A supplementary adverse experience report (using FDA Form 3500, MedWatch) will be submitted as soon as possible following any adverse experience meeting the above criteria. Completed FDA Forms 3500 will be mailed to the Clinical Research Pharmacist (Albuquerque CSPCRPCC) with a copy to each of the Study Co-Chairmen's offices.

If an adverse experience is fatal or life-threatening, an immediate telephone report is required and a written report (using FDA Form 3500) must follow within 72 hours. All such reports (written and telephone) will be submitted to both the Clinical Research Pharmacist and the Study Co-Chairmen.

Reports of alarming adverse experiences will be screened by the Clinical Research Pharmacist and Study Co-Chairmen. All investigators will be notified of any report suggesting new hazards. The Clinical Research Pharmacist will provide periodic summaries of all alarming adverse experiences to the Palo Alto CSPCC, the Data Safety and Monitoring Board and if applicable, the FDA.

A serious adverse experience is defined as any experience that suggests a significant hazard, contraindication, side effect, or precaution. With respect to human clinical experiences, this includes any experience that 1) is fatal or life-threatening, 2) is permanently or substantially disabling, 3) requires hospitalization, 4) prolongs an existing hospitalization; or is 5) a congenital anomaly; 6) cancer; or 7) the result of an overdose.

An unexpected adverse experience is defined as any experience not identified in the Investigator's Brochure or elsewhere in the protocol, is thought by the reporter to be unanticipated in nature, intensity or frequency, or to have potential relevance to the overall safety of the study medication.

XI. Substudies and Ancillary Studies

A. Introduction

There are two types of substudies: ancillary studies and databank studies. Databank studies are based on data collected in the course of the main study while ancillary studies consist of additional data collected beyond that in the primary protocol. It is the express intent of the Steering Committee and the sponsoring federal agencies to derive the maximum amount of scientific information from the BEST database via primary endpoint analyses and to encourage the development of Ancillary Studies, Databank and Substudies. An equal opportunity will exist among the BEST units to participate in the analysis and presentation of the data pertaining to the major objectives of the study as well as to the proposal and performance of Ancillary Studies, Databank and Substudies. Participation in these activities will be open equally to the Principal Investigators of all BEST sites, the Coordinating Center, the Central Clinical Office and the NHLBI Program Office. With the approval of the Principal Investigators, the Co-Investigators at the various sites are encouraged to participate in this process.

In order to assure that these activities will proceed with a high level of scientific merit and with fairness to all participants, the Publications and Substudies Subcommittee will review applications for nonprotocol studies, will coordinate the formation of the writing groups on each topic, and will make recommendations to the Steering Committee for both of these activities.

B. Ancillary studies

An ancillary study uses BEST participants in an investigation which is not described in the BEST protocol and involves data which is not collected as part of the routine BEST data set. Such studies may be carried out independently by the applicant investigators or in conjunction with other BEST investigators or units, and require independent (non BEST) funding.

Ancillary studies must be approved by the Steering Committee on the recommendation of Substudies Subcommittee. All applications for ancillary studies must be submitted in writing to that Subcommittee. They will be assessed on the appropriateness of the question(s) being asked and must assure that the investigation will not interfere with the main objectives of BEST. They should be implemented only after recruitment and performance in the main study are satisfactory at the relevant clinical centers. Studies may not begin until approval is transmitted from the Coordinating Center.

C. Databank studies

A databank study utilizes data which has been routinely collected as part of the main BEST study in order to answer questions other than those proposed in the main protocol. It involves only the analysis of data and is generally not funded since it uses resources at the Coordinating Center. However, such studies must be approved by the Steering Committee at the recommendation of the Substudies Subcommittee. All applications for databank studies will be graded by the Subcommittee for scientific merit and the appropriateness of the question being asked, and must assure that the timing of publication will not interfere with the main objectives of BEST.

D. Other ("Non-BEST") projects

Simultaneous participation of the BEST participants in an unrelated study is strongly discouraged since this may result in interference with BEST objectives or place demands on the participant that may diminish his/her availability, cooperation or willingness to participate in additional BEST-related studies. In certain circumstances, it may be desirable, for clinical reasons, to enter a BEST participant into a compassionate use protocol in order that this participant may receive an investigational drug or device. This decision will be made by the Principal Investigator of a Clinical Site and will be based on the clinical needs of the participant. Prior approval is not required.

However, the principal investigator is required to notify the Coordinating Center of this action within 10 days. Simultaneous participation of a BEST participant in a non-BEST prospective investigation requires the prior approval of the Executive Committee.

E. Data storage and analysis

Data forms will be stored at the Coordinating Center and data will be entered into the computer system. Data will be analyzed at the Coordinating Center unless other arrangements have been approved by the Substudies Committee.

F. Application Review Process

The Substudies committee will review proposals at each of the semi-annual meetings as well as between meetings as necessary. If several applications for similar substudies (Ancillary or Databank) are received, the Substudies committee will request the applicants to resolve differences in their proposals and resubmit a joint application. If irreconcilable differences exist between the applications or if the applicants are unwilling to cooperate, the Substudies committee will individually grade the applications by scientific merit and feasibility. It is implicit that performance of additional studies must not undermine the major objectives of BEST at any site.

In order to assure that all sites have an equal opportunity to develop and participate in the analyses, proposals will then be circulated through the Chairman of the Substudies Committee to each of the Principal Investigators to invite their participation. In the case of Substudies, the proposer (the first name on the application) will recommend participants and their level of responsibility to the Steering Committee. Once the concept of a substudy has been approved, the protocol will be developed by the particular investigator(s). In the case of Ancillary or Databank studies, the proposer (the first name on the application) will be responsible for selecting participants and their level of responsibility.

Applications from non-BEST investigators or institutions are welcomed but will be accorded secondary status should a similar application be received from a qualified BEST investigator.

XII. Publication Policy

The Publications subcommittee will review all publications following the guidelines given below and report its recommendations to the Steering Committee.

A. Data analysis and release of results

The scientific integrity of the project requires that the data from all BEST sites be analyzed study-wide and reported as such. Thus, an individual center is not expected to report the data collected from its center alone. The development of reports of data from individual sites for the determination of institutional variability is the prerogative of the Steering Committee. Additionally, all presentations and publications are expected to protect the integrity of the major objective(s) of the study; data that break the blind will not be presented prior to the release of mainline results. Recommendations as to the timing of presentation of such endpoint data and the meetings at which they might be presented will be given by the Steering Committee.

B. Review process

Each paper or abstract, as described below, must be submitted to the appropriate Subcommittee for review of its appropriateness and scientific merit prior to submission. The Subcommittee may recommend changes to the authors and will finally submit its recommendations to the Steering Committee for approval.

C. Primary outcome papers

The primary outcome papers of BEST are papers that present outcome data (such as mortality or the efficacy of the BEST agent in reducing heart failure) for the BEST participant group. The determination of whether or not a particular analysis represents a primary outcome will be made by the Steering Committee on the recommendation of the Publications Subcommittee. Authorship on primary outcome manuscripts will be "The BEST Investigators". For such manuscripts, there will be an appendix containing the names of the organizational units, their Principal Investigators and Co-Investigators. Organizational units will include the Clinical Sites, the Central Research Pharmacy, the Coordinating Center, Central Laboratory, the Central Clinical Office and the Project Office. The Data and Safety Monitoring Board for the manuscript will also be listed under those designations in the appendix.

D. Other study papers, abstracts and presentations

All studies other than those designated as "Primary Outcome" fall within this category. Papers or abstracts resulting from these studies will have named authorship of individuals involved, ending with the phrase "for the BEST Investigators." In addition, papers will have an appendix containing the names of the organizational units, their Principal Investigators and Co-Investigators and other individuals participating in the study. Units will include the Clinical Sites, the Central Research Pharmacy, the Coordinating Center, Central Laboratory, the Central Clinical Office and the Project Office. All papers and abstracts must be approved by the Publications Committee before they are submitted.

It is possible that in certain instances BEST may be asked to contribute papers to workshops, symposia, volumes, etc. The individuals to work on such requests should be appointed by the Executive Committee, but where time permits, a proposal will be circulated soliciting other participants as in the case of other study papers as described in the Application Review Process.

XIII. Close-out Procedures

BEST may terminate at the planned target of 1.5 years after the last participant has been randomized, or at an earlier or later date if the circumstances warrant. Plans for close-out must be made in the absence of any knowledge as to these circumstances and must therefore be fairly flexible, yet specific enough to be useful.

Regardless of the circumstances for termination of the trial, our objectives in closing out the study are as follows:

- To evaluate as fully and accurately as the data permit the effect of the beta-blocker on all-cause mortality and to make these results public as expeditiously as possible.
 - To fulfill our ethical and humane obligations to the BEST study participants.
- To promote the scientific value of study data as fully as possible.

Close-out procedures including recommendations for further patient care will be developed by the Steering Committee. Regardless of the timing and circumstances of the end of the study, close-out will proceed in two stages:

- Interim period for analysis and documentation of study results.
 - Debriefing of participants and dissemination of study results.

A. Interim

Every attempt will be made to reduce to an absolute minimum the interval between the completion of data collection and the release of the study results. We expect to take about 3 to 4 months to compile the final results paper for an appropriate journal.

B. Reporting of study results

The study results will be released to the participating physicians, referring physicians, patients and the general medical community.

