Patients will be randomized to treatment with either bucindolol or placebo in a double blind design that will be stratified based upon etiology of heart failure, gender, ejection fraction, race and the hospital at which they are treated. Etiology of congestive heart failure will be divided into presence or absence of coronary artery disease (CAD). For the purpose of the study, coronary artery disease will be defined as either: (1) a history of previous myocardial infarction (MI), diagnosed by ECG (Qwaves) or enzymes, (2) evidence of significant obstruction, greater than 70% diameter luminal narrowing of at least one major epicardial artery with corresponding regional wall motion abnormality, (3) an unequivocally positive stress perfusion study demonstrating coronary artery disease, (4) an exercise stress test in a patient with an interpretable ECG (i.e. no BBB, LVH, or ST-T changes at baseline, and not on digitalis), who demonstrates provokable ischemia (i.e. 2 mm or more of flat or down sloping ST - depression at 80 msec after the J-point). In the case of positive ETT and normal angiography, the patient will be classified as non-CAD. While coronary angiography or stress perfusion is not mandated for entry, the investigator is expected to determine the etiology of ventricular dysfunction as part of the patient's routine care. Following randomization, patients will be started on a twice daily treatment regimen consisting of either bucindolol 3.0 mg, or placebo. Doses of drug will be titrated over a 5-9 week period as tolerated with the ultimate goal of reaching a dose of bucindolol of 200 mg PO daily (100 mg PO twice daily) for patients weighing greater than or equal to 75 kg at randomization, and 100 mg daily (50 mg PO twice daily) for patients weighing less than 75 kg at randomization.

D. Study size and duration

The recruitment will extend for 3 years and there will be a minimum follow-up of 1.5 years (*note: patient accrual was extended by 7 months*). The study will have a 85% power to detect a 25% mortality reduction. Based on these considerations, a target sample size of 2800 randomized patients with equal numbers assigned to each treatment group is needed (see Appendix A for sample size calculation).

E. Drug Rationale

Rationale for drug selection

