APPENDIX A - SAMPLE SIZE AND RATIONALE

A. Overview

The primary objective of this study is to evaluate the effectiveness of beta-blocker therapy in reducing all cause mortality in patients with moderate to severe congestive heart failure who are receiving concomitant optimal medical therapy. The study is planned as a double-blind, two-arm clinical trial of NYHA class III-IV patients with ejection fraction ≤ 0.35 randomized to either the placebo or beta-blocker (bucindolol) groups. The primary endpoint is time to death. We estimate that 2800 patients will be required to detect with 85% power a 25% annual mortality reduction with bucindolol therapy, taking into account several factors that tend to reduce power. Our approach to sample size was a) to calculate the required number of patients for a range of reasonable design assumptions; b) decide on a sample size; and c) carry out a sensitivity analysis for the fixed sample size in order to evaluate the impact of misspecification of assumptions on the power of the trial.

While there are many approaches to calculating sample size for time-to-event data, the method of Lakatos^{81, 82} was used because it provides estimates of sample size for tests based on the logrank statistic after adjusting for complex trial characteristics such as staggered accrual, time-varying hazard ratios, a lag in treatment effect, losses to followup, noncompliance, and heart transplantation. The adjustment is accomplished by assuming a placebo death rate and percent mortality reduction with treatment (or equivalently a hazard reduction) in a "perfect" trial and then adjusting the rates based on a schedule over time of losses, noncompliance, etc. The observed mortality reduction after adjustment will be lower than before adjustment.

Although randomization will be stratified by hospital site, presence/absence of coronary artery disease, ejection fraction, race and gender, we did not incorporate stratification in the sample size calculations and instead assumed average rates across strata.

B. Assumptions

The target sample size of 2800 patients (1400 per group) was based on the following assumptions (annual rates for mortality, losses to follow-up, noncompliance, and heart transplantation refer to patient years on study, not calendar time):

- 1. Significance level (Type I error) of 5%, two-sided
- 2. **Power** (sensitivity) of 85%

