- 3. **Patient accrual** assumed to be uniform over a 3 year intake period, 18 month minimum followup, 3 year average followup, total study length of 4.5 years.
- 4. Annual mortality rate of 15% in the placebo group (prior to adjusting for noncompliance, losses etc.) which is conservative based on similar previous studies of heart failure^{5,6,8,9,63}. These studies are summarized in the table below, with our proposed study BEST as the last entry.

Study	Severity of Heart Failure	Mortality Rate	
VA V-HeFT II ⁸ enalapril group	NYHA class II & III with <1% class IV	16.5% annually	
SOLVD ⁶ enalapril group	mild to moderate	12% year 1 10% year 2 13% year 3 7% year 4	
CONSENSUS ⁵ enalapril group	severe, NYHA class IV	36% year 1	
PROMISE ⁶³	moderate to severe (all patients) NYHA class III NYHA class IV	32% year 1 27% year 1 40% year 1	
BEST (proposal)	moderate to severe $EF \le 35$, NYHA class III-IV	15% annually	

(The rates shown for SOLVD are approximations estimated from the cumulative rates extrapolated from Kaplan-Meier curves).

Patients in PROMISE had a high mortality rate despite angiotensin converting enzyme inhibitors. However, PROMISE randomized patients to inotropic therapy and therefore only the sickest patients were entered. Due to some investigator bias against randomizing the sickest patients to a beta-adrenergic blocking agent, a conservative annual placebo group mortality of 15% is assumed in the proposed study.

- 5. **Mortality reduction** The study target is set for detecting a reduction in annual mortality of 25%, i.e. from 15% to 11.25% before adjusting for losses, noncompliance, etc. The design implications of these factors are discussed below. The planning committee decided that a 25% reduction in annual mortality under ideal experimental conditions was the smallest effect size of clinical interest upon which they were willing to base the trial. It is estimated below that the adjusted cumulative 4.5 year mortality rates would be 35% and 30% in the placebo and beta-blocker groups, respectively, which results in an adjusted cumulative 4.5 year mortality reduction of 15%. The need for adjustment is due to the following complicating assumptions.
- Lag An initial 3 month lag in treatment benefit is assumed (i.e., death rates in the two groups were assumed to be equal during the initial 3 months of patient follow-up) since 5-9 weeks are needed to titrate patients onto bucindolol.

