Figure 3.4 is included to show that placebo mortality rates and percent mortality reduction have pronounced effects on the sensitivity of the trial. By comparison, misspecification of the noncompliance rate has a much smaller effect. If the noncompliance rate is 16% and percent reduction with treatment is 25% as assumed for this trial, and if the unadjusted placebo rate is an unexpectedly low 10%, then power is reduced to 57%. Because the projected placebo mortality rate of 15% is considered conservative in a population of moderate to severe heart failure patients, we show that a higher mortality rate of 20%, which may be obtained, offers some protection against misspecification of other assumptions. If the mortality reduction is 20% versus the desired 25% and the noncompliance is 16% with a placebo mortality rate of 15% then the power of the trial is reduced to 60%. The study investigators chose 25% to be the effect size of clinical interest in designing this trial.

D. Study Duration

This study is planned for a total duration of 4.5 years in 90 medical centers. Three years will be needed to recruit 2800 patients at an average rate of approximately 1 patient per month per center. A minimum followup of 18 months was considered necessary to observe the effects of bucindolol. Other smaller studies previously discussed have shown therapeutic benefit within this period of time. Other combinations of intake period and study duration were considered such as a shorter trial with more centers and a longer trial with fewer centers, but the advantages did not appear to outweigh the disadvantages in terms of complexity and cost.

E. Contingency Plans

If the cumulative mortality rate in the control group is substantially lower than expected by the end of the second year of the study, the sample size may have to be increased and/or follow-up extended to observe a sufficient number of deaths, or the need for a study reevaluated in the light of the low control mortality.

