5. DESCRIPTION OF TREATMENT GROUPS

5.01 Outline of Study Design

The primary objective of this prospective, randomized, double-blind study is to evaluate the effect of β -adrenergic blockade on all cause mortality in patients with moderate to severe chronic heart failure in spite of conventional medical therapy. The basic study design is outlined in Figure 1.

[FIGURE 1]

```
Patient Eligible and Consenting? \rightarrow No \rightarrow EXCLUDE

\downarrow

Yes

\downarrow

RANDOMIZE

\downarrow

Bucindolol HCI

Placebo
```

Patients screened by study personnel and found to be eligible for participation in the study will be stratified according to (1) the hospital site and (2) the presence or absence of coronary artery disease. Patients will be treated and followed serially until death, refusal to continue study follow-up or termination of the study. Approximately 2,800 patients will enter the study during the three year enrollment period. The study will have a total duration of 4.5 years.

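### The study duration, average follow-up, expected deaths and power in Appendices A and B were not updated for the 7-month accrual extension and no longer describe the adopted schedule

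*Protocol*

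**What the plan says.** The current text describes the trial's length in two ways.

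**Places that lead to about 61 months**
- Section II.D: "The recruitment will extend for 3 years and there will be a minimum follow-up of 1.5 years (*note: patient accrual was extended by 7 months".
- Section XIII: "BEST may terminate at the planned target of 1.5 years after the last participant has been randomized". The same sentence allows an earlier or later end if circumstances call for it.
- The preface entry for the June 1999 edition says that follow-up was lengthened by 7 months along with accrual.

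**Places that still give 3 years of intake, 54 months in total, or both**
- Appendix A, section B, item 3: uniform entry over 3 years, with "18 month minimum followup, 3 year average followup, total study length of 4.5 years".
- Appendix A, Table 1: 3-year intake and 4.5-year trial, giving 916 deaths and 2790 patients at 85% power.
- Appendix A, section D: "This study is planned for a total duration of 4.5 years in 90 medical centers". The same section calls an 18-month minimum follow-up necessary.
- Appendix B, 5.01: a 3-year enrolment period, and "The study will have a total duration of 4.5 years".
- Appendix B, 9.01(c): the maintenance dispensing table stops at the 54-month visit.

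**The concern.** While accrual was 36 months, the two descriptions were the same: 36 + 18 = 54 months. With 43 months they cannot both hold. A reader who takes the 4.5-year total from either appendix gets a trial that breaks the 18-month minimum in II.D and in Appendix A itself.

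The length of the trial determines how many deaths enter the primary logrank test (section VIII.B.2), so it determines the power. The only death count attached to the chosen design is 916. Anyone who needs an expected total for planning or monitoring would take it from there, and it belongs to a schedule that is no longer in use.

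**Working it through.** **Inputs, all from Appendix A section B unless stated**
- "Significance level (Type I error) of 5%, two-sided"; "The target sample size of 2800 patients (1400 per group").
- Placebo mortality 15% a year, bucindolol 11.25%; no effect in the first 3 months.
- Loss 1% a year in each group.
- Noncompliance on bucindolol 10% in year 1, then 2% a year, with noncompliers reverting to the placebo death rate.
- Transplants 1.85% and 0.37% a year from year 2, with 80% of them averting a death.
- Accrual 36 + 7 = 43 months (II.D). Uniform entry of all 2800 over 43 months is my assumption.

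**Step 1. Calendar arithmetic**
- Close 18 months after the last entry: 43 + 18 = 61 months (5.083 years).
- Follow-up of the last patient if the trial stops at 54 months: 54 − 43 = 11 months.
- Average potential follow-up under uniform entry is total length minus half the accrual period:
  - original: 4.5 − 3/2 = 3.0 years
  - 43 months of accrual, 54-month stop: 4.5 − 3.583/2 = 2.71 years
  - 43 months of accrual, 61-month stop: 5.083 − 3.583/2 = 3.29 years

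**Step 2. Reproduce the plan's own figures**

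I used a Lakatos-type calculation in short time steps. Each annual rate p becomes a hazard −ln(1 − p). From year 2 the death hazard is lowered by 0.8 × the transplant rate. Patients leave administratively as the stop date reaches them, and the logrank statistic is accumulated over the steps.

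| Quantity | Protocol | Recomputed |
|---|---|---|
| Deaths needed for 85% power | 916 | 912 |
| Patients needed | 2790 | 2756 |
| Power, no transplants | 96% | 96.2% |
| Power, 6-month lag | 72% | 72.0% |
| Power, placebo rate 10% | 57% | 55.6% |
| Power, 20% reduction | 60% | 60.8% |
| Power, 25% noncompliance | 81% | 79.4% |

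All are within 2 power points or about 1.2%, so the model is a fair stand-in for the plan's own.

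**Step 3. Change only the schedule, with 2800 patients**

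| Accrual / total length | Average follow-up | Deaths | Power |
|---|---|---|---|
| 36 / 54 months (original) | 3.0 y | 926 | 85.6% |
| 43 / 61 months (adopted) | 3.29 y | 990 | 87.6% |
| 43 / 54 months (literal appendix total) | 2.71 y | 848 | 82.5% |

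A second run with a finer time step gave the same deaths to within one, and powers of 85.7%, 87.8% and 82.7%.

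**Step 4. Cross-check with a constant hazard ratio**

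For 916 deaths at 85% power the implied ratio is exp(−2 × (1.960 + 1.036)/√916) = exp(−0.198) = 0.820. Scaling the deaths in step 3 to the plan's own count (× 916/926 × 2800/2790) gives 983 for the adopted schedule and 842 for the 54-month stop. Power is Φ(0.198 × √D/2 − 1.960):
- D = 983: Φ(3.104 − 1.960) = 87.4%
- D = 842: Φ(2.873 − 1.960) = 81.9%

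**Step 5. Sensitivity to enrolment**

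With 2700 patients over 43 months, the 61-month close gives 955 deaths and 86.4% power, and the 54-month stop gives 818 and 81.1%. With 2500 patients the figures are 884 and 83.7%, against 757 and 78.1%.

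**The case against.** The best defence is that the document does settle the end date. Sections II.D and XIII, supported by the preface, all lead to about 61 months. In Appendix A the 4.5 years is simply 3 + 1.5 and appears next to the 18-month minimum. Appendix A records how 2800 was chosen, so its inputs should stay as they were. The end date was also meant to be flexible: section XIII allows it to move, and Appendix A section E foresees longer follow-up if control mortality is low. On the adopted schedule, power rises.

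Most of this stands, and it rules out two stronger readings.

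- **Two rival stopping dates.** A reader might infer that the protocol offers a 54-month and a 61-month stop, about 140 deaths and 5 power points apart. No section pairs 43 months of accrual with a 54-month stop. Appendix B 5.01 itself follows patients to death, refusal or study termination. The 54-month figures show only what a literal reading would cost.
- **Alpha spent too early.** A reader might infer that the Lan-DeMets boundary in VIII.C would be used up at 916 deaths, before close-out. The protocol does not tie information to 916 deaths or state any information scale, and that detail may properly sit in a monitoring plan that is not shown.

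The defence does not remove the stale figures. II.D carries a note on the extension. The appendices that state the duration, average follow-up, deaths and power carry none, and Appendix B 5.01 is an operating instruction to pharmacies, with no role as a record of the sizing.

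**Conclusion.** The protocol is wrong as written, to a modest extent. The adopted schedule is about 61 months. The stated 4.5-year total, 3-year average follow-up, 916 deaths and 85% power describe the original sizing. On the original rates the adopted schedule gives about 3.3 years, 980 to 990 deaths and 87 to 88% power, roughly 2 to 3 points above the stated figure. Read literally, a 54-month stop would give about 840 to 850 deaths and 82 to 83%, some 2 to 3 points below it, and would break the 18-month minimum.

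These figures assume that all 2800 patients enter uniformly over 43 months and that the Appendix A rates hold. Lower enrolment reduces them, as step 5 shows. The validity of the primary test is not in question.

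One point is conditional. If the monitoring plan measures information against a planned number of deaths, 916 would be about 93% of the updated total (916/983), and the updated total is the one to use.

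**What to change.** - **Appendix A:** keep the existing assumptions and Table 1, dated and labelled as the basis for 2800. Add the current schedule: 43 months of accrual and close-out 18 months after the last randomisation, about 61 months in total. Give the average follow-up, expected deaths and power from a rerun of the Lakatos program with the actual accrual pattern.
- **Appendix B 5.01:** correct the enrolment period and total duration to match.
- **Appendix B 9.01(c):** the dispensing table ends at 54 months, while patients entered in the first 7 months would reach that visit before a 61-month close. The table and the schedule must be reconciled.
- **Monitoring plan, if it counts information in deaths:** use the updated total, fixed without reference to results by treatment.

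The cost is wording and one rerun. It adds no patients, and no follow-up beyond the extension already adopted.
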